### 7.3.1 Clinical Assessments and Procedures

### 7.3.2 Tumor Response Criteria

Tumour response will be evaluated according to the RECIST v1.1 (see [Appendix 14.5](#)) (<http://www.eortc.be/Recist/documents/RECISTGuidelines.pdf>) and clinical criteria (Eisenhauer et al, 2009). Disease progression will be defined as per RECIST version 1.1 guidelines on radiological, clinical, or symptomatic progression.

Evaluation of response by RECIST v1.1 criteria should be performed at baseline and then at 6-week intervals beginning at Week 6. Immune-related response criteria (irRECIST) (see [Appendix 14.6](#)) may be used for clinical management of subjects, but will not be used for OR evaluation (other than as an exploratory endpoint). Therefore RECIST 1.1 will be adapted to account for the unique tumor response characteristics seen with immunotherapy treatment. Immunotherapeutic agents such as pembrolizumab may produce antitumor effects by potentiating endogenous cancer-specific immune responses. The response patterns seen with such an approach may extend beyond the typical time course of responses seen with cytotoxic agents, and can manifest a clinical response after an initial increase in tumor burden or even the appearance of new lesions. Standard RECIST may not provide an accurate response assessment of immunotherapeutic agents such as pembrolizumab. Therefore, RECIST 1.1 will be used with the following adaptations:

If radiologic imaging verifies initial PD, tumor assessment should be repeated  $\geq 4$  weeks later in order to confirm PD with the option of continuing treatment per the conditions stated below, while awaiting radiologic confirmation of progression.

If repeat imaging shows  $< 20\%$  or  $< 5$  mm absolute increase in tumor burden compared to nadir, stable or improved previous new lesion (if identified as cause for initial PD), and stable/improved non-target disease (if identified as cause for initial PD), treatment may be continued / resumed.

If repeat imaging confirms PD due to any of the scenarios listed below, subjects will be discontinued from study treatment\*.

In determining whether or not the tumor burden has increased or decreased, the Investigator should consider all target lesions as well as non-target lesions.

Scenarios where PD is confirmed at repeat imaging:

- Tumor burden remains  $\geq 20\%$  and at least 5 mm absolute increase compared to nadir

- Non-target disease resulting in initial PD is worse (qualitative)

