## 14.6 Immune Related Response Criteria (irRECIST)

**Table 14.6 Imaging and Treatment after First Radiologic Evidence of PD**

	Clinically Stable		Clinically Unstable	
	Imaging	Treatment	Imaging	Treatment
1st radiologic evidence of PD by RECIST 1.1	Repeat imaging at $\geq$ 4 weeks at site to confirm PD	May continue study treatment at the local site Investigator's discretion while awaiting confirmatory tumor imaging by site by irRECIST.	Repeat imaging at $\geq$ 4 weeks to confirm PD per physician discretion only	Discontinue treatment
Repeat tumor imaging confirms PD by irRECIST at the local site	No additional imaging required	Discontinue treatment (exception is possible upon consultation with sponsor)	No additional imaging required	N/A
Repeat tumor imaging shows SD, PR or CR by irRECIST by the local site	Continue regularly scheduled imaging assessments	Continue study treatment at the local site Investigator's discretion	Continue regularly scheduled imaging assessments	May restart study treatment if condition has improved and/or clinically stable per Investigator's discretion. Next tumor image should occur according to the every 6 week ( $\pm$ 7 days) imaging schedule

If tumor imaging shows initial disease progression, the Investigator may elect to continue treatment, repeat imaging  $\geq$  4 weeks later and assess tumor response or confirmed progression per irRECIST (see [Section 7.3.2](#) and [Table 14.6](#) above).

irRECIST is RECIST 1.1 adapted as described in the Table 14.6 to account for the unique tumor response seen with immunotherapeutic drugs. irRECIST may be used by the Investigator to assess tumor response and progression, and make treatment decisions. This data will be collected in the clinical database.

- In determining whether or not the tumor burden has increased or decreased, the Investigator should consider all target lesions as well as non-target lesions. Subjects who

are deemed clinically unstable are not required to have repeat tumor imaging for confirmation.

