11.1 Primary Efficacy Analysis

The primary efficacy endpoint is the overall response rate (ORR), which is defined as the proportion of subjects demonstrating complete response (CR) or partial response (PR) based on RECIST1.1.

The evaluation of response based on RECIST 1.1 will be performed at baseline and then at 6- week intervals beginning at week 6. The best response is the best response recorded from the start of study treatment until the first disease progression based on RECIST1.1 or start of new cancer therapy, whichever occurs earlier. The best response will be determined programmatically based on the investigator's assessment of response at each time point, using the following rules:

Table 1 Best Overall Response When Confirmation of Complete Response and Partial Response is Required

Overall Response First Timepoint	Overall Response Subsequent Timepoint	Best Overall Response
CR	CR	CR
CR	PR	SD, PD or PR ^a
CR	SD	SD provided minimum criteria for SD duration was met, otherwise, PD
CR	PD	SD provided minimum criteria for SD duration was met, otherwise, PD
CR	NE	SD provided minimum criteria for SD duration was met, otherwise, NE
PR	CR	PR
PR	PR	PR
PR	SD	SD
PR	PD	SD provided minimum criteria for SD duration was met, otherwise, PD
PR	NE	SD provided minimum criteria for SD duration was met, otherwise, NE
NE	NE	NE

a: If a CR is truly met at first time point, then any disease seen at a subsequent time point, even disease meeting PR criteria relative to baseline, makes the disease PD at that point (since disease must have reappeared after CR). Best response would depend on whether minimum duration for SD was met. However, sometimes 'CR' may be claimed when subsequent scans suggest small lesions were likely still present and in fact the patient had PR, not CR at the first time point. Under these circumstances, the original CR should be changed to PR and the best response is PR.

CR=complete response; NE=not evaluable; PD=progressive disease; PR=partial response; SD=stable disease.

Note: the minimum criteria for SD is the interval of 5 weeks (35 days).

As further clarification:

- To be assigned CR or PR as the best response, it must be confirmed no less than 4 weeks (28 days) from the time of the initial CR or PR;

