- If a best response of CR or PR cannot be established, stable disease (SD) can be assigned as a best response if the SD assessment is at least 5 weeks [35 days] after the first dose of study treatment (Note: a minimum interval of 5 weeks was chosen because tumor imaging is scheduled every 6 weeks +/- 1 week).
- If the CR is not confirmed, and a best response of PR can not be established, then the best response will be SD if the CR, PR, or SD assessment is at least 5 weeks after the first dose of study treatment.
- If the PR is not confirmed, and a best response of CR can not be established, then the best response will be SD if the CR, PR or SD assessment is at least 5 weeks after the first dose of study treatment.

- If the CR or PR is not confirmed, and the assessment date does not meet SD criteria (a minimum interval of 5 weeks after the first dose of study treatment), then the best response will depend on the subsequent assessments: if an assessment of PD follows CR or PR, then the best response will be PD; if subjects are lost to follow up after only one CR or PR assessment, then the best response will be considered as NE.
- If the SD assessment is less than 5 weeks after the first dose of study treatment and a best response of CR and PR could not be established, the best response will depend on the subsequent assessments: if an assessment of PD follows the SD, then the best response will be PD; if subjects are lost to follow up after the SD assessment, then the best response will be considered as NE.
- PD is considered the best response when PD is documented and a best response of CR, PR, or SD could not be established. Clinical progression alone in the absence of radiological confirmation is not a progression event in this analysis.
- NE is considered the best response when PD has not been documented and a best response of CR, PR, or SD could not be established.

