11.3.1 ORR Based on irRECIST

The best response based on irRECIST is the best response recorded from the start of study treatment until the disease progression (the PD per RECIST1.1 or the PD confirmed by irRECIST, whichever is later) or start of new anti-cancer therapy, whichever occurs earlier. The best response will be determined programmatically in the same way as the best response based on RECIST 1.1 (Section 11.1) except the following:

- Confirmed PD is considered the best response when PD is documented and confirmed by irRECIST and a best response of CR, PR, or SD could not be established before documentation of PD. Clinical progression alone in the absence of radiological confirmation is not a progression event in this analysis.
- Unconfirmed PD is considered the best response when PD is documented but not confirmed and a best response of CR, PR, or SD could not be established before documentation of PD. Unconfirmed PD will be further categorized as PD with further assessment but not confirmed by irRECIST vs PD without further assessment to confirm.

The best response based on irRECIST will be summarized for the Evaluable, All Treated and Per-Protocol populations. Calculation of ORR and CRR based on irRECIST are the same as those based on RECIST 1.1 in Section 11.1. In the summary, ORR, CRR, DCR, the number (%) of subjects with the best overall response of CR, PR, SD, confirmation PD, unconfirmed PD, and NE will be included, and an exact 95% confidence interval will be computed for the rates of ORR, CRR and DCR.

Listing of PD based on RECIST 1.1 and whether PD is confirmed by irRECIST at next visit will be provided.

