11.3.2. PFS Based on irRECIST

Progression-free survival based on irRECIST is defined as the time from the date of the first dose until the PD or death due to any cause, whichever occurs first. The determination of PD as PFS event will be as following:

- For subjects with confirmed PD, the first PD (prior to the confirmation) that is confirmed by irRECIST will be the PFS event;
- For subjects with PD but not confirmed by irRECIST and no further disease assessment after the last unconfirmed PD, the last unconfirmed PD will be the PFS event.

For subjects who have neither progressed nor died, PFS will be censored at the date of the last adequate assessment of CR, PR or SD on/prior to the start of new anti-cancer systemic therapy and before missed visits (if 2 or more scheduled assessments are missed). Assignment of event and censoring date is similar with those of the PFS based on radiological assessment RECIST 1.1 (as defined in Section 11.2.4) with the exception that PD is determined differently for subjects with confirmed PD and subjects with unconfirmed PD as stated above.

The PFS based on irRECIST will be summarized descriptively and graphically using the Kaplan-Meier method for the Evaluable, All Treated and PP populations. The Kaplan-Meier estimate for the median, first and third quartiles will be determined along with 95% confidence intervals. The Brookmeyer-Crowley method will be used for the confidence interval calculation. The Kaplan-Meier estimate of PFS rate at landmark times including but not limited to 3, 6 and 12 months will be summarized. The Kaplan-Meier Plot of PFS will be provided for the Evaluable and All Treated population. Listing of PFS based on irRECIST will be provided for the All Treated population.

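### Read literally, SAP 11.3.1 drops some responses that follow an unconfirmed first progression from the exploratory irRECIST ORR

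*SAP*

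**What the plan says.** Protocol 7.3.2 explains why standard RECIST is adapted: under immunotherapy a subject "can manifest a clinical response after an initial increase in tumor burden or even the appearance of new lesions". Table 14.6 in Protocol Appendix 14.6 provides for this case. One of its rows is "Repeat tumor imaging shows SD, PR or CR by irRECIST by the local site", and for it treatment may go on and scheduled imaging continues. ORR by irRECIST is part of the first exploratory objective (Protocol 3.3, SAP 2.3).

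SAP 11.3.1 takes over the RECIST 1.1 algorithm of SAP 11.1 with listed exceptions. Three parts matter here.

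- **Window.** Best response is taken up to the disease progression, defined as "the PD per RECIST1.1 or the PD confirmed by irRECIST, whichever is later", or up to new anti-cancer therapy if that is earlier. In 11.1 the window runs "from the start of study treatment until the first disease progression based on RECIST1.1 or start of new cancer therapy".
- **Unconfirmed PD.** A subject is put in this class if "PD is documented but not confirmed and a best response of CR, PR, or SD could not be established before documentation of PD".
- **Sub-categories.** Unconfirmed PD is split into "PD with further assessment but not confirmed by irRECIST vs PD without further assessment to confirm".

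The matching rule in 11.1 has no time limit: "PD is considered the best response when PD is documented and a best response of CR, PR, or SD could not be established".

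For irRECIST PFS, SAP 11.3.2 says that "the first PD (prior to the confirmation) that is confirmed by irRECIST will be the PFS event". It makes an unconfirmed PD an event only if no assessment follows it.

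**The concern.** The irRECIST ORR exists to show whether responses appear after an apparent early progression. Two pieces of wording in 11.3.1 work against that.

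1. The time limit at the end of the unconfirmed-PD rule looks only at what was established ahead of the PD. A subject whose first scan shows PD has nothing before it, so a later confirmed response does not help. The first sub-category shows that rescanned subjects are meant to fall in this class.
2. The window takes the later of two dates. If PD is never confirmed, there is only one date, the RECIST 1.1 PD, and the window closes at the flare.

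If the rule is programmed as written, some late responders are reported as non-responders. A finding of few or no extra responses under irRECIST could then come partly from the rule rather than from the data. The same subject can also be progression-free for irRECIST PFS while holding a best response of unconfirmed PD.

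**Working it through.** The plan gives no figure to reproduce; this is a check of a classification rule.

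**Inputs.** Scans are every 6 weeks from Week 6. A response is confirmed at least 28 days after it is first seen, so PR at two consecutive scans counts. SD needs at least 35 days from first dose, so SD at a Week 6 scan on schedule (day 42) counts. All three come from SAP 11.1.

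**Readings compared.**
- Window *literal*: ends at the later of the RECIST 1.1 PD and the confirmed PD, and at the RECIST 1.1 PD if none is confirmed. Window *open*: stays open until a confirmed PD.
- Limit *literal*: CR, PR or SD must come before the first PD. *Fallback*: PD is used only if nothing better is established in the window, as in 11.1.

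**Sequences.**
- A: PD Week 6 (unconfirmed), PR, PR, no later PD
- B: as A, then a later confirmed PD
- C: SD Week 6, PD Week 12 (unconfirmed), PR, PR, no later PD
- D: as C, then a later confirmed PD
- E: PD Week 6, no further scan

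| | RECIST 1.1 (11.1) | Window literal, limit literal | Window literal, fallback | Window open, limit literal | Window open, fallback |
|---|---|---|---|---|---|
| A | PD | unconfirmed PD | unconfirmed PD | unconfirmed PD | PR |
| B | PD | unconfirmed PD | PR | unconfirmed PD | PR |
| C | SD | SD | SD | PR | PR |
| D | SD | PR | PR | PR | PR |
| E | PD | unconfirmed PD | unconfirmed PD | unconfirmed PD | unconfirmed PD |

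**What the table shows.**
- A loses its response unless both pieces of wording are read more loosely than they are written.
- B loses it through the time limit alone. If the PD in that limit is taken to mean the later, confirmed one, B is PR.
- C is never classed unconfirmed PD, but under the literal window its response is lost and it is classed SD.
- D is a PR on every reading of 11.3.1, although it is only SD under RECIST 1.1.
- E is correctly unconfirmed PD throughout.

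**Against SAP 11.3.2.** In A the PD is unconfirmed but further assessments follow, so it is not an event and PFS is censored at the last PR. Under 11.3.1 the same subject has a best response of unconfirmed PD.

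**Size per affected subject**, with the full planned evaluable numbers as denominators:
- Melanoma: 1/29 = 3.4 percentage points
- TNBC: 1/41 = 2.4 percentage points

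**The case against.** The strongest reply is that the text is ambiguous rather than wrong. Section 11.3.1 keeps the 11.1 algorithm, in which PD is a fallback, and nothing expressly withdraws the rule that two PRs at least 28 days apart make a PR. The section is also silent on where the window ends if no PD is confirmed; a sympathetic programmer would leave it open and count A as PR. This stands only in part. The time limit appears in a list introduced as exceptions to 11.1, so a programmer would be right to code it. The fallback reading alone does not rescue A, because the window must also be read generously.

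A second reply is that the loss is narrow and visible. SD at the Week 6 scan takes a subject out of the unconfirmed-PD rule. Many responders may progress later: the pembrolizumab monotherapy study in TNBC cited in Protocol 4.3.1 had a median DoR of 6.3 months. A later confirmed PD would bring a subject like C back as PR. The unconfirmed group is tabulated separately, and response at each visit is listed (SAP 11.1), so cases could be traced. All of this is fair and limits the harm. It does not make the headline rate right, and with SD before the flare the literal window drops exactly those whose response lasts.

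A third reply is that the analysis is exploratory and SAP 11.3 says only that it may be run. That stands, and it sets the weight of the point.

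**Conclusion.** The point holds in a limited form. Read literally, 11.3.1 drops late responders by two routes: an unconfirmed PD that comes before any CR, PR or SD is established, and a PD that is never confirmed. It does not match 11.3.2. Each affected subject costs 3.4 points (melanoma) or 2.4 points (TNBC) of irRECIST ORR. The total effect cannot be given, because the documents do not state how often a flare is followed by response.

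A reader might infer more than the documents support:
- *That irRECIST ORR cannot count any late response, must equal the RECIST 1.1 ORR, or leaves the exploratory objective unanswerable.* Sequence D refutes this on every reading.
- *That a subject with PD at the first scan who then responds is rescued by a later confirmed PD.* This depends on which PD the time limit means.
- *That a missed responder should be judged against the success counts of 4 and 5.* Those belong to the RECIST 1.1 primary test. Protocol 7.3.2 keeps irRECIST out of response evaluation except as an exploratory endpoint, and no decision uses it.

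The primary ORR, the interim rule and the error rates are unaffected. The conclusion assumes that 11.3.1 would be programmed as written and that the full planned evaluable numbers are reached. The point should be corrected before analysis, but it does not threaten the trial's main result.

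**What to change.** In SAP 11.3.1:

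1. End the response window at the progression date of 11.3.2, which is the first PD later confirmed by irRECIST, or the last unconfirmed PD with no further assessment. If there is no such date, end it at the last adequate assessment. If new anti-cancer therapy starts earlier, end it there.
2. In both PD rules, confirmed and unconfirmed, replace the closing time limit with a requirement that refers to that window.
3. Assign unconfirmed PD only when no confirmed CR or PR, and no SD, is established in that window.

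With these changes A to D are all PR and E stays unconfirmed PD, and the ORR and PFS rules share one progression date. That date also covers a responder whose final PD is never rescanned, which Protocol 7.3.2 permits for clinically unstable subjects.

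The cost is a few lines of SAP text and one programming rule. No new data are needed: Appendix 14.6 continues scheduled imaging after an unconfirmed PD and sends the irRECIST data to the clinical database, and SAP 11.3 has confirmation status collected on the CRF.

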11.3.2. PFS Based on irRECIST

Progression-free survival based on irRECIST is defined as the time from the date of the first dose until the PD or death due to any cause, whichever occurs first. The determination of PD as PFS event will be as following:

- For subjects with confirmed PD, the first PD (prior to the confirmation) that is confirmed by irRECIST will be the PFS event;
- For subjects with PD but not confirmed by irRECIST and no further disease assessment after the last unconfirmed PD, the last unconfirmed PD will be the PFS event.

For subjects who have neither progressed nor died, PFS will be censored at the date of the last adequate assessment of CR, PR or SD on/prior to the start of new anti-cancer systemic therapy and before missed visits (if 2 or more scheduled assessments are missed). Assignment of event and censoring date is similar with those of the PFS based on radiological assessment RECIST 1.1 (as defined in Section 11.2.4) with the exception that PD is determined differently for subjects with confirmed PD and subjects with unconfirmed PD as stated above.

The PFS based on irRECIST will be summarized descriptively and graphically using the Kaplan-Meier method for the Evaluable, All Treated and PP populations. The Kaplan-Meier estimate for the median, first and third quartiles will be determined along with 95% confidence intervals. The Brookmeyer-Crowley method will be used for the confidence interval calculation. The Kaplan-Meier estimate of PFS rate at landmark times including but not limited to 3, 6 and 12 months will be summarized. The Kaplan-Meier Plot of PFS will be provided for the Evaluable and All Treated population. Listing of PFS based on irRECIST will be provided for the All Treated population.

11.4 Exploratory Efficacy Analysis Based on Biomarker Data

Exploratory efficacy analysis will be conducted with the biomarker data including, but not limited to the following:

- Correlate levels of baseline serum anti- β -glucan antibody (ABA) with objective response and treatment outcomes;
- Correlate changes in immune cell activation markers with objective response and treatment outcome;
- In tumor biopsies, correlate changes in the tumor immune microenvironment including TILs (Tumor-infiltrating Lymphocytes) and tumor-infiltrating myeloid cells with objective response and treatment outcome; and/or
- Correlate PD-L1 expression in tumor biopsy samples (in tumor cells and myeloid cells) with objective response and treatment outcome.

Due to the exploratory nature of the analysis, the list of tables and figures for the efficacy analysis with biomarker data will be determined after conducting the analysis.

12 SAFETY ANALYSIS

Safety measurements include adverse events, serious adverse events, death, ECOG performance status, laboratory tests (hematology, clinical chemistry, coagulation, and urinalysis), vital signs, physical examination, and ECG measurements. Unless stated otherwise, all safety analyses will be based on the All Treated population, and will be conducted separately for each tumor type. Listings of safety data will include both tumor types.

